### **C.20.c. Patient Cost and Utilization.**

All resource utilization and cost data will come from Decision Support System (DSS) data (or equivalent database if the VA data storage locations change before the end of the study), including the DSS Outpatient (OPAT) National Data Extract (NDE), the DSS NDE SAS Pharmacy Dataset, and the DSS Inpatient Discharge Extract File (DISCH). We will measure VA outpatient and inpatient utilization and costs by treatment or control over 18 months. Outpatient encounters will be categorized using clinic stop codes into primary care visits, specialty care visits, and other outpatient care (laboratory, radiology, surgery, nursing, and all other clinical visit and ancillary services and encounters not already mentioned), as well as a count of total encounters (unique CLSTOPS) and total costs (OCST\_TOT). We will also examine hypertension-related outpatient pharmacy prescription counts and costs using an identification method developed in the HINTS study (SAS algorithm of HTN-related outpatient drugs developed by [name], Puget Sound VA), in order to compare them to total outpatient pharmacy costs (DISP\_COST plus ACT\_Cost). The utilization most likely to be affected by the intervention will be outpatient and pharmacy-related. For comparability with other studies, however, we will also examine inpatient utilization and costs. Inpatient encounters will include whether there was any inpatient care in the study period, total days in the hospital (DISDAY minus ADMITDAY, DAYS), and total inpatient costs (DCST\_TOT). We will also use diagnostic codes to categorize inpatient stays that are hypertension related. The analysis will focus on differences in utilization and costs in the study period but we also will examine costs in the 18 months pre-intervention to check for temporal trends. Specific variables outlined above represent applicable variables as of the time of the initial protocol submission. Because of changing VA data structures, the precise variable names may change over the course of the study. In addition we will evaluate costs from the perspective of both patient and society.

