##### D.6.b. Analysis.

The primary objective of the cost-effectiveness analysis will be to estimate the cost per unit difference in effectiveness. The incremental cost effectiveness ratio (ICER) will be calculated as the difference in the average cost per patient between the treatment and control arm divided by the difference in the units of mmHg between the treatment and control arms:

$$ICER = \frac{AVERAGE\ COST_{t=x} - AVERAGE\ COST_{t=0}}{Average\ Reduction\ mmHg_{t=x} - Average\ Reduction\ mmHg_{t=0}}$$

Because we will take an all-cost approach, that is, we assume that any costs unrelated to blood pressure or the intervention will be neutral between the treatment and control group, we will carefully examine the data for outliers. For example, there may be high inpatient costs for patients in the intervention group that are attributable to non-hypertension related comorbidities, necessitating a consideration of this in the analysis. As such, in addition to a consideration of all resource utilization costs described, we will run sensitivity analysis in which we will (1) use diagnostic codes in the inpatient files in order to attribute inpatient utilization to treatment of comorbidities associated with chronic hypertension and/or diabetes, running a sub analysis only on this type of inpatient care; (2) remove patients who are outliers and (3) consider outpatient costs and outpatient HTN-related pharmacy costs exclusively. In addition, we will also perform sensitivity analysis of the ICER calculated on two samples: all patients randomized (complying with the intention to treat principles and a subset of all patients who completed the intervention. Sensitivity analyses will also be performed on types of costs: intervention costs, resource utilization costs, and total costs (intervention costs plus resource utilization costs). If there are no differences in resource utilization across arms, we will simply include the intervention

costs in the ICER calculation. All dollars will be expressed in 2011 dollars, using the Consumer Price Index for Medical Care for medical items or Consumer Price Index for other items.

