We will use stochastic methods to evaluate variability associated with the cost-effectiveness ratio. If the difference in SBP is significantly higher in an intervention arm relative to the standard care arm, the 95% confidence interval for the base-case cost-effectiveness ratio will be computed with nonparametric bootstrapping using the bias-corrected percentile method (1,000 repetitions). The bootstrapping procedure will allow us to use limited information to estimate the sampling distribution of mean costs per patient, which then will allow us to make inference about the true population sampling distribution of mean costs without making strong distributional assumptions. Using bootstrapped confidence intervals will help us bind our estimates in a way that reduces the influence of outliers. This procedure is relevant for thinking about implementation effects of the intervention, when there will be much larger sample sizes and a ICER not limited by small sample properties.

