### **J.1.d. Supplemental Data Extraction.**

In order to complete health economic, medication adherence, and exploratory analyses, we will extract data from the VA electronic health record or related linked administrative data on healthcare events for the full sample from the study. With appropriate informed consent and HIPAA authorization, clinical and utilization data from VA electronic health record or related linked administrative data may be obtained for the period prior to study enrollment.

The extracted data will be stored on a VA HSR&D server that is compliant with regulations described in VA Directive 6500 and located on the VA FISMA certified network. The servers are located within the VA protected environment (i.e. behind the VA fire wall) and are physically located within the secured server room at the offices of the Durham VAMC HSR&D Center of Excellence. Physical access to the servers is limited to authorized VA OI&T personnel in accordance with VA directive 6500. Only HSR&D study staff at the Durham VAMC will have access to data stored on the server. All staff has and maintain VA required training, maintain study data exclusively on HSR&D servers, follow accepted security practices such as locking computer with CTRL-ALT-DEL when not at the computer, and adhere to other regulations laid out in VA Directive 6500. Destruction of data will be done in accordance with all VA and VHA records disposition requirements.

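### The ICER cost difference is set out without covariates although pre-intervention costs are to be examined, which gives up precision on the utilization-cost comparison

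*Protocol*

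**What the plan says.** In D.6.b the ICER is "calculated as the difference in the average cost per patient between the treatment and control arm", divided by the between-arm difference in mmHg reduction. No regression model and no covariate is named for cost. The interval is a nonparametric bootstrap of that ratio with 1,000 repetitions.

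C.20.c fixes the outcome window: "We will measure VA outpatient and inpatient utilization and costs by treatment or control over 18 months". It adds that the focus is on study-period differences, "but we also will examine costs in the 18 months pre-intervention to check for temporal trends". No other section gives the pre-period costs a role. J.1.d covers access to them, subject to HIPAA authorization and patient consent: "clinical and utilization data from VA electronic health record or related linked administrative data may be obtained for the period prior to study enrollment".

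D.6.b also states the scope, with neutrality assumed across the two arms: "Because we will take an all-cost approach, that is, we assume that any costs unrelated to blood pressure or the intervention will be neutral". It then sets a rule on what goes into the ratio: "If there are no differences in resource utilization across arms, we will simply include the intervention" costs.

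The other outcomes are treated differently. D.3 sizes the systolic blood pressure (SBP) comparison by ANCOVA, and the models in D.2, D.4 and D.5 all include the stratification variables, which C.6 gives as diabetes status and baseline SBP stratum.

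**The concern.** All-cause VA cost over 18 months is likely to be skewed and to persist within a patient, and D.6.b itself expects outliers. If one arm happens to receive more patients who were already heavy users, that imbalance passes into the difference in means. A bootstrap describes the resulting uncertainty but does not remove it. A patient's own cost over a matching earlier period is a natural covariate, and the protocol already plans to examine it.

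Two things are at stake. One is the precision of the utilization-cost difference. The other is the rule that drops utilization costs when the arms do not differ: the noisier the comparison, the easier it is to miss a real difference and leave those costs out of the ICER.

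**Working it through.** **1. What baseline adjustment is worth in the protocol's own SBP calculation.** Inputs from D.3: difference 5 mmHg, SD 17.5, correlation 0.4, attrition 15%, power 80%, type I error 5% (taken as two-sided).

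- Unadjusted: n per arm = 2 × [17.5 × (1.960 + 0.842) / 5]² = 192.3.
- ANCOVA: 192.3 × (1 − 0.4²) = 161.5, so 162 per arm.
- Attrition: 162 / 0.85 = 190.6, so 191 per arm or 382 in total. The planned 400 covers this with a small margin.
- With 200 × 0.85 = 170 per arm, power is 82.0% with baseline adjustment and 75.0% without.

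So the protocol takes the benefit of a baseline value for SBP.

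**2. The same step for utilization cost.** The protocol gives no cost SD and no pre/post cost correlation r, so r is an assumption. The ratio of adjusted to raw standard error is √(1 − r²), whatever the SD. The equivalent number per arm is 200 / (1 − r²).

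| Assumed r | SE ratio | SE reduction | Equivalent n per arm (actual 200) |
|---|---|---|---|
| 0.2 | 0.980 | 2% | 208 |
| 0.3 | 0.954 | 5% | 220 |
| 0.4 | 0.917 | 8% | 238 |
| 0.5 | 0.866 | 13% | 267 |
| 0.6 | 0.800 | 20% | 312 |

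As an illustration only, with an assumed SD of $20,000 the raw SE is 20,000 × √(2/200) = $2,000. Adjustment gives $1,960 at r = 0.2 and $1,600 at r = 0.6.

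**3. Does the formula survive skewed costs?** Lognormal costs were simulated with 200 per arm and no true difference, 5,000 trials per setting. With an assumed coefficient of variation of 1.5, the SE ratios at r = 0.3, 0.5 and 0.7 were 0.95, 0.86 and 0.69. With 2.5 they were 0.92, 0.81 and 0.64. The gain was as large as the formula predicts or larger, and neither estimator showed material bias.

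**4. What adjustment cannot reach.** Intervention costs (C.20.b: staff time, training, home monitors) arise only during the study and have no pre-period counterpart. The ICER denominator is also untouched. On the D.3 inputs its SE is 17.5 × √0.84 × √(2/170) = 1.74 mmHg. If the observed difference is 5 mmHg, its 95% interval is 5 ± 1.96 × 1.74, or about 1.6 to 8.4 mmHg.

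**The case against.** The best reply is that nothing here is wrong. A difference in arithmetic mean cost is a standard ICER numerator, it is unbiased under randomization, and D.8 applies intention to treat to all analyses. The covariates of a secondary cost model are often left to an analysis plan, and the opening of section D allows methods to change. D.6.b does not use the word unadjusted, and C.21.i plans a comorbidity index for risk adjustment.

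Much of this stands. It rules out calling the plan biased. It does not remove the point: the protocol is not silent, since it writes down a cost contrast without covariates and gives the pre-period costs another use. C.21.i is not tied to D.6.b.

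The limits on the gain also stand. It is small at low correlation. It is close to nil for the reported ratio if only intervention costs enter. Pre-enrollment data depend on consent and HIPAA authorization, and C.3.a requires a primary care visit only within the last year, so a full 18-month pre-period is not assured for every patient. The cost-effectiveness question itself arises only if the intervention proves effective (A.1.c, D.6).

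A reader might infer that cost is the noisiest quantity in the trial, or that the numerator governs the width of the ICER interval. The protocol gives no cost SD to support either, and the denominator alone spans roughly a fivefold range. Nor does the plan rely on discarding outliers: the base case keeps all utilization costs, and outlier removal is one of several sensitivity runs.

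**Conclusion.** The point holds as one of lost efficiency and avoidable exposure to chance imbalance, not of bias. D.6.b leaves out a baseline value that the protocol already intends to examine, and the stratification factors that its other outcome models include. If r lies between 0.2 and 0.6, the SE of the utilization-cost difference would fall by about 2% to 20%, equivalent to 208 to 312 patients per arm instead of 200. That range rests wholly on the assumed r. The ICER interval would generally narrow by less, because intervention costs and the SBP denominator are unaffected. The same comparison settles whether utilization costs are counted, so its precision matters beyond the interval itself.

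**What to change.** In D.6.b, estimate the mean utilization-cost difference by linear regression of 18-month utilization cost on arm, pre-intervention cost, diabetes status and baseline SBP stratum. A linear model keeps the arithmetic mean difference as the target. Add the between-arm difference in intervention cost to form the numerator. Refit the whole calculation in each bootstrap replicate, and keep the unadjusted difference as a sensitivity analysis. Where a patient lacks the full 18-month pre-period, use the pre-period cost that is available. In C.20.c, name the pre-intervention cost as a covariate as well as a check on trends.

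The cost is wording and slightly more analysis work, with no new visits or patients and no data beyond those C.20.c already plans to examine. The downside is little return if the correlation turns out low or if only intervention costs enter the ICER.

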### **C.20.d. Adherence to Blood Pressure Medication.**

We will assess adherence using **prescription refill data**. These data will be extracted from the Durham VistA (electronic health record) system or national VA pharmacy databases that contain pharmacy information

from the VA electronic health record. Commonly used in pharmacoepidemiology, refill data are used to estimate the supply of medications patients have and are often expressed as a Medication Possession Ratio (MPR). In this study, we will use ReComp, which was developed and validated using pharmacy refill data. ReComp is more flexible than previous measures in handling longer prescription periods for chronic cardiovascular medications. ReComp also accounts for multiple dimensions of adherence behavior (e.g., late fills, use of overstocked medication) and is more precise than previous refill approaches when used in repeated measures over short time periods. We will utilize ReComp to measure adherence with antihypertensive medication [considered together for adherence]. An aggregate ReComp-based MRP measure will be calculated for each patient by averaging ReComp MPR for individual drug classes covering six month time intervals beginning 1 year prior to patient randomization and continuing during the 18 months of the intervention or booster control. Other methods for calculating medication adherence using prescription refill data may also be examined using the same data.

## **C. 21. Measures to Increase Understanding of Intervention Mechanisms/Potential Covariates**

### **C.21.a. Self Reported Medication Adherence.**

For **self-reported medication adherence**, we selected a modification of a 4-item measure developed by Morisky et al. Respondents are asked to rate their medication-taking behaviors on a scale ranging from 1 (strongly agree) to 4 (strongly disagree). Higher scores reflect lower adherence. The measure will be administered at baseline and at the 6-, 12-, and 18-month study visits. Self-reported adherence is complementary to the secondary outcome measure of medication adherence based on prescription refill data. Endorsing any of the items is considered to indicate nonadherence.

### **C.21.b. Self-efficacy.**

Self-efficacy involves a "judgment of one's abilities to produce given attainments." In the Health Decision Model as discussed in section B.8., individuals who believe they possess the skills necessary to achieve goals are more likely to adopt healthy behaviors. Additionally, self-efficacy has been well studied and applied to diabetes interventions, usually through fostering confidence in behavior change (e.g., weight reduction, physical activity) that enhance outcomes such as glucose control. We expect the intervention will improve patients' self-efficacy to change behaviors related to BP control. Thus, we will measure both behavior change and self-efficacy at baseline, 6-, 12-, and 18-month study visits. Self-efficacy for hypertension will be measured using the measures utilized in V-STITCH.

### **C.21.c. Exercise.**

One of the goals of the intervention will be to increase the amount of leisure-time exercise performed by those patients who are not exercising to appropriate standards. Leisure-time activity will be measured by the Short International Physical Activity Questionnaire (IPAQ). The measure will be administered at baseline and at the 6-, 12-, and 18-month study visits.

### **C.21.d. Body Mass Index.**

The sentinel impact of diet on control of both glucose and blood pressure is weight loss, which leads to significant improvement in both those parameters. Therefore, we will use weight as a proxy for success in changing diet, and we will measure weight at baseline, 6-, 12-, and 18-month study visits. We will measure height at baseline, allowing us to use body mass index as an estimate of appropriateness of weight for each individual.

### **C.21.e. Literacy.**

At baseline we will measure health-related literacy by using the Rapid Estimate of Adult Literacy in Medicine (REALM), a brief, well-validated measure of health-related literacy that correlates >0.9 with the criterion standard measure. REALM is associated both with gold standard reading evaluations and, in a recent meta-

analysis, with a number of chronic disease outcomes. If a patient is unable (e.g. patient did not have his or her reading glasses with them) or wishes not to complete the REALM (requires reading a series of words) at baseline, we will offer the REALM at a subsequent study visit.

#### **C.21.f. Social Support.**

At baseline, two questions previously used in clinical trials at the Durham VA Medical Center will be used to measure overall social support, which is associated with better chronic illness self-management and BP control.

**C.21.g. EQ-5D -5L-** is a standardized measure of health status. It provides a simple descriptive profile and a single index value that addresses: mobility, self-care, usual activities, pain/discomfort, anxiety/depression.

#### **C.21.h. Demographics.**

We will measure a number of demographic factors that may affect response to the intervention, including race, ethnicity, age, marital status, education level, gender, adequacy of annual income, and number of people living in the household. All will be measured at baseline by patient self-report. If over the course of the study a patient notes a change in this information (e.g. marital status changes), that information may be recorded and used in study analyses.

#### **C.21.i. Comorbidities for Risk Adjustment, Pharmaceuticals, and Smoking Status.**

Medical comorbidities and presence of end-stage organ damage influence BP and glycemic control in many ways. The presence of comorbid illnesses will increase patients' medical regimen complexity. This increase in complexity results in patients' increased difficulty remembering and adhering to their medication regimens. Additionally, certain medical comorbidities and end-stage organ damage are indicators of severity of both diabetes and hypertension. Thus, we will assess comorbidities by using the Deyo modification of the Charlson comorbidity index [or equivalent risk adjustment index] (calculated for the year prior to enrollment), utilizing data obtained from **Inpatient and Outpatient Medical SAS Datasets** housed at the VA Austin Information Technology Center [or other equivalent centralized VA data system or the VHA electronic health record]. We will also measure self-reported smoking and alcohol use at baseline, 6-, 12-, and 18-month study visits.

#### **C.21.j. Patient Perception of Organization of their Primary Care.**

We will assess patient perception of provision of chronic care with the Patient Assessment of Chronic Illness Care (PACIC). The PACIC is a validated 20-item instrument that measures specific actions or qualities of care that patients report they have experienced in the delivery system. Patients grade each item along a 5-point Likert Scale. The PACIC produces five subscales corresponding to five components of the CCM: 1) patient activation; 2) delivery system design/decision support; 3) goal setting; 4) problem-solving/contextual counseling; and 5) follow-up/coordination. Six items will be added to measure delivery of the 5-As of patient-centered counseling (ask, advise, agree, assist, and arrange) which represents hypothesized optimum self-management support. The measure will be administered at baseline and 18-month study visits.

#### **C.21.k. Berlin Questionnaire – Evaluation of risk of having sleep apnea.**

We will use the Berlin questionnaire at the 6 month study visit. For participants who miss their 6 month study visit the interventionist will conduct it prior to the sleep apnea encounter. The questionnaire consists of 3 categories related to the risk of having sleep apnea. Patients can be classified into High Risk or Low Risk based on their responses to the individual items and their overall scores in the symptom categories. Use of the questionnaire is described in the following paper: (Netzer NC, Stoohs RA, Netzer CM, et al. Using the Berlin Questionnaire to identify patients at risk for the sleep apnea syndrome. *Ann Intern Med.* 1999; 131: 485–491).

## C.22. Data Quality

Use of the electronic data management system, described in section J.1 below, will aid the research assistant (RA) conducting study visit to monitor which data collection instruments and questions have been completed by the patient. Though the computerized auditing procedure, the RA will determine if all questions have been answered. If not, the subject will be given the opportunity to answer questions. As with all study components, the study patient will have the opportunity to decline to answer any questions. Before the end of the study visit, the RA will complete a checklist to ensure that all measurements are completed.

Study implementation and quality assurance methods that we will be employed include: 1) careful scheduling and thorough, timely monitoring of the planned visit schedule to be certain that complete visits do occur; 2) collection of contact information for each participant at each visit; 3) prompt contact and rescheduling of missed study visits; and 4) review and documentation of the reasons for missed visits that do occur. We will also review individual patient data promptly to identify problems or missing values that can be completed by follow-up.

